### 591 **More Rare yet Serious Risks:**

592 The risk of **venous thromboembolism** (VTE) is clearly increased with HRT, with the risk  
593 influenced by age and preparation/type therapy. In the Women's Health Initiative Trial, the risk  
594 of VTE was greater with combined estrogen + progestin (HRT) (HR 2.06) than with conjugated  
595 equine estrogen alone (HR 1.32), with both risk rates reduced in the 50-59 year olds (estimated  
596 excess events 9-10/1,000 for HRT and 3-4/1000 for ERT) (Rossouw, J.E., et al., *Risks and*  
597 *benefits of estrogen plus progestin in healthy postmenopausal women: principal results From the*  
598 *Women's Health Initiative randomized controlled trial*. *Jama*, 2002. **288**(3): p. 321-33. Lyytinen,  
599 H., E. Pukkala, and O. Ylikorkala, *Breast cancer risk in postmenopausal women using estradiol-*  
600 *progestogen therapy*. *Obstet Gynecol*, 2009. **113**(1): p. 65-73).

601 Notably, the risk for VTE was significantly reduced by the use of transdermal estradiol in case  
602 control studies (HR 0.9 compared with HR 4.2 in those taking oral estrogen) (Scarabin, P.Y., et  
603 al., *Effects of oral and transdermal estrogen/progesterone regimens on blood coagulation and*  
604 *fibrinolysis in postmenopausal women. A randomized controlled trial*. *Arterioscler Thromb Vasc*  
605 *Biol*, 1997. **17**(11): p. 3071-8.

606 Both HRT and ERT increase the risk of **stroke** Hendrix, S.L., et al., *Effects of conjugated equine*  
607 *estrogen on stroke in the Women's Health Initiative*. *Circulation*, 2006. **113**(20): p. 2425-34).  
608 Not surprisingly, the increased risk is age-dependent (excess attributable risk 1 case per 5000  
609 women years in the 50-59 year olds vs 4.5 in the whole Women's Health Initiative Study group),  
610 largely reflecting the increased risk of stroke with aging.

611 **Breast Cancer** – Both HRT and ERT increase the risk of breast cancer (although the impact of  
612 duration and timing of therapy are still uncertain). Focusing on ERT (which decreases the risk  
613 compared with HRT by almost a factor of four) (Beral, V., *Breast cancer and hormone-*  
614 *replacement therapy in the Million Women Study*. *Lancet*, 2003. **362**(9382): p. 419-27), an early  
615 meta-analysis concluded that no increased risk of breast cancer occurred if estrogen alone was  
616 administered for less than five years (*Breast cancer and hormone replacement therapy:*  
617 *collaborative reanalysis of data from 51 epidemiological studies of 52,705 women with breast*  
618 *cancer and 108,411 women without breast cancer. Collaborative Group on Hormonal Factors in*  
619 *Breast Cancer*. *Lancet*, 1997. **350**(9084): p. 1047-59).

620 A subsequent meta-analysis reported a relative risk increase of 3.1%/year Taking the worst  
621 case scenario, the risk in a 50-54 year old woman who takes estradiol alone for five years would  
622 increase from 13/1000 women (with no ERT) to 14.94/1000 women (Endocrine Society, in  
623 press). Thus, the risk of exposure to one year of ERT would be insubstantial. **Ovarian cancer** –  
624 Long term use of ERT alone increases the risk of ovarian cancer, with an attributable risk of 0.7  
625 per 1000 women per 5 years of use (Lacey, J.V., Jr., et al., *Menopausal hormone replacement*  
626 *therapy and risk of ovarian cancer*. *Jama*, 2002. **288**(3): p. 334-41.

627 326. Morch, L.S., et al., *Hormone therapy and ovarian cancer*. *Jama*, 2009. **302**(3): p. 298-  
628 305).

629 **Endometrial Cancer** - Exposure to unopposed estrogen increases the risk of endometrial cancer  
630 two fold (Grady, D., et al., *Hormone replacement therapy and endometrial cancer risk: a meta-*  
631 *analysis*. *Obstet Gynecol*, 1995. **85**(2): p. 304-13). Use of a progestin prevents both endometrial  
632 hyperplasia and the increased risk of endometrial cancer (Lethaby, A., et al., *Hormone*  
633 *replacement therapy in postmenopausal women: endometrial hyperplasia and irregular*  
634 *bleeding*. *Cochrane Database Syst Rev*, 2000(2): p. CD000402).

635 Although sequential use of progestin does not protect the endometrium to the same degree as  
636 continuous combined, long cycle sequential progestin (q 3 month progestin) (as is proposed for  
637 use in our study) has not been associated with increased risk of endometrial cancer (Furness, S.,  
638 et al., *Hormone therapy in postmenopausal women and risk of endometrial hyperplasia*.  
639 *Cochrane Database Syst Rev*, 2009(2): p. CD000402; Odmark, I.S., et al., *Endometrial safety*  
640 *and bleeding pattern during a five-year treatment with long-cycle hormone therapy*. *Menopause*,  
641 2005. **12**(6): p. 699-707).

642 **Risks Associated with Brachial Artery Imaging:** There are no significant risks associated with  
643 the ultrasound assessment of brachial artery imaging, though the inflation of the pneumatic cuff  
644 to 200 mmHg for 5 mins may be painful. Side effects associated with the sublingual  
645 administration of nitroglycerine include headache, dizziness, flushing or restlessness.

646 **Psychological Risks:** The structured interviews to assess current and lifetime psychiatric illness  
647 and prior trauma may be associated with some psychological distress. Some items in the  
648 questionnaires may provoke some negative emotion in some individuals. There is also the risk a  
649 woman will experience the onset of a depression episode or have a worsening of depressive  
650 symptoms over the course of the 12-month intervention period that would go undetected or  
651 untreated.

652  
653 Standard risks associated with venipuncture include syncope, discomfort, nausea, bruising.  
654 Although measures are taken to protect the privacy of every participant, there is a remote risk of  
655 breach of confidentiality/loss of privacy.

656

#### 657 **Protection Against Risk:**

658 • Risks associated with Estrogen and progesterone are minimized in our protocol by i) including  
659 only young, medically healthy perimenopausal women undergoing a natural menopause  
660 transition; ii) a thorough gynecological exam and medical history conducted by study  
661 gynecologist [name] to ensure that all women are eligible candidates for ERT; 3) the use of  
662 intermittent micronized progesterone (200 mg/day for 12 days every 3 months) to eliminate any  
663 increased risk of endometrial disorder associated with ERT and to avoid exposure to other  
664 progestins; 4) the requirement for a normal mammogram and breast exam at study entry; 5) the  
665 exclusion of women with a family history indicative of increased breast or ovarian cancer risk  
666 (see exclusion criteria in A.4.4. above); 5) exposure to estradiol for only 12 months since short-  
667 term exposure (< 3-5 yrs) has not been shown to be associated with an increased risk of breast  
668 cancer; 6) the frequent assessment of vitals, side effects and depression symptoms (months  
669 1,2,4,6,8,10 and 12); 7) the provision of instruction and instructional sheet (enclosed for review)  
670 for performing monthly self-breast exams; 8) provision of a patient information sheet with the  
671 instruction to call the study doctors immediately if any of the following symptoms are

672 experienced: severe or prolonged vaginal bleeding, severe headaches, changes in vision or  
673 speech, mental depression, nervousness, or suicidal thoughts, dizziness or faintness, pains in  
674 calves or chest, sudden shortness of breath, or detection of a breast lump; (enclosed for review);  
675 8) the development of a safety monitoring plan (see below); and 9) monitoring for adverse events  
676 by a Data and Safety Monitoring Committee.  
677

678 While risks associated with the endothelial flow mediated dilatation assessment may include  
679 discomfort or pain associated with inflation of the pneumatic cuff, the pain lasts only a few  
680 minutes and there is no risk of tissue damage during 5 minutes of forearm ischemia. Moreover,  
681 numerous studies in our laboratory using the submaximal effort tourniquet procedure to assess  
682 voluntary pain tolerance following inflation of a pneumatic arm cuff to 200 mmHg have reported  
683 that the average voluntary tolerance for women is approximately 650 seconds (> 10 mins), twice  
684 as long as the time required in the present study. Risks of dizziness associated with  
685 nitroglycerine will naturally be minimized since subjects will be in the supine position and  
686 instructed to stand up slowly. While headache may develop, our prior experience with this  
687 procedure is that headaches were mild, short-lived, and did not interfere with function.

688

689 Psychological risks associated with the interviews and stress testing are minimized via the use of  
690 clinically trained interviewers and highly competent and professional staff. Frequent contact  
691 with subjects and frequent assessment of depressive symptoms (months 1, 2, 4, 8, 10, and 12)  
692 will minimize the risk that a worsening of depressive symptoms would go undetected. Risks  
693 associated with phlebotomy will be minimized by using sterile materials, by applying pressure to  
694 the skin upon removal of the needle, and by placing each subject in the reclined position to  
695 minimize risk of syncope. Risks of loss of confidentiality will be minimized by the use of  
696 subject codes linked to all data and by maintaining the file linking the subject code to the name  
697 in a separate secure location. All databases will be stored on a secure, HIPAA compliant  
698 network. The server is backed up nightly. The database is also protected by logins and  
699 passwords required to open the system. Different levels of privileges are granted to different  
700 users. This study will use a web-based, secure, password protected access to the database.  
701 Passwords will be changed every 90 days.

702

### 703 **Data Monitoring and Analysis**

704 The safety of the study will be monitored by a **Data and Safety Monitoring Board (DSMB)**.  
705 This will ensure the independent oversight of issues related to safety and adverse events. This  
706 DSMB will consist of 4 members: a Cardiologist, a Psychiatrist, a Biostatistician, and a  
707 Gynecologist.

#### 708 **I. Grading of Adverse Events (AEs)**

709 Adverse events will be classified according to severity as either mild, moderate, or severe.  
710

711 **Mild AE:** is defined as having no effect on activities of daily living such as transient light  
712 headedness or sweating with venipuncture; breast tenderness, mild skin irritation; or something  
713 of equal significance that requires no medical intervention and is of marginal clinical relevance.  
714

715 **Moderate AE:** would be associated with temporary (minutes to a few days) disruption in  
716 activities of daily living such as temporary loss of consciousness with venipuncture; a worsening  
717 of migraines or headache that require bed rest, an increase in depression symptoms consistent  
718 with mild DEP mood (CES-D scores = 10 - 15), excess sleepiness or fatigue that resolves with  
719 additional rest, or something of equal significance.  
720

721 **Severe AE:** would cause serious disruption in daily activities of living and may or may not  
722 require hospitalization. Examples of such events would include a thromboembolic event, breast  
723 carcinoma, an increase in blood pressure consistent with Stage 2 hypertension, any  
724 cardiovascular event, any event that is permanently disabling, any event requiring hospitalization  
725 or is life threatening, severe mood impairment or failed suicide attempt or something of equal  
726 significance. Death would also be considered a severe AE.  
727

## 728 **II. Monitoring and Reporting of Adverse Events (AEs)**

729 The study coordinator will monitor side effects and AEs at all study visits (on a monthly basis  
730 initially and then quarterly) and report all side effects as well as any significant mood  
731 deterioration (see below) directly to [name] following study visits. Side effects consistent  
732 with moderate or severe AEs or that are troublesome to the subject, or evidence of mood  
733 deterioration reported by telephone, will also be immediately reported to [name]. [name]  
734 will ensure that [name] or [name] are consulted within 24-hours. Staff will be  
735 specifically trained to monitor the CES-D rating scales for scores > 10 or for endorsement of  
736 suicidal ideation and report any such occurrence immediately. In the case of mood deterioration,  
737 [name] will determine the next course of action, including a reassessment of mood in two  
738 weeks or more urgently if deemed to be clinically required. [name] will be the responsible  
739 physician to determine the next course of action involving medical side effects (e.g., continue in  
740 protocol, exclude and refer for treatment).

741

742 The PIs, [name] and [name] will review all protocol data at monthly meetings, including  
743 enrollment and retention statistics and aggregate reports of side effects/AEs. As the contact PI,  
744 [name] will be the one responsible one to report any individual occurrence of an AE to the  
745 Chair of the DSMB according to the guidelines established at the initial DSMB meeting (e.g. the  
746 DSMB may require the reporting of any serious adverse event on an individual basis and in an  
747 on-going fashion). She will also report all moderate or severe AEs to the IRB and CTSC within  
748 1 week. Since we are employing a marketed pharmaceutical product (i.e., a non-IND study),  
749 unexpected Serious AEs will be also be reported to the FDA Medwatch Program. The NIMH  
750 program officer will be notified of any study modifications or suspension imposed by the DSMB  
751 or local IRB in response to an AE.

752 [name] will also report all AEs graded as moderate or severe to the study gynecologist, who  
753 will maintain a secured, password protected file linking subject ID to subject name and will also

754 receive the randomization code by subject ID from Investigational Drug Services. In the event  
755 that it is medically necessary to become unblinded to treatment assignment, he will be able to do  
756 so very quickly.

757 We also have a plan for the monitoring of medical conditions that may emerge during the course  
758 of the 12 month study requiring treatment or withdrawal. The development of hypertension or  
759 hyperlipidemia represent the most likely medical conditions that may emerge over a 12 month  
760 interval in perimenopausal women. Our protocol allows for the frequent monitoring of BP levels  
761 (months 1, 2, 4, 6, 8, 10, and 12) throughout the protocol. Consistent with JNC 7 guidelines, the  
762 detection of BP levels during the study in the Stage 1 HTN range (140 – 159 mmHg SBP or 90 –  
763 99 mmHg DBP) will prompt monthly reassessments of BP to confirm BP status, and a review of  
764 the American Heart Association (AHA) dietary and physical activity guidelines with the subject.  
765 If the average BP over any 3 consecutive months remains in the Stage 1 HTN range, the subject  
766 will be withdrawn and referred for treatment. Detection of BP levels consistent with Stage 2  
767 HTN at any point will prompt immediate withdrawal and referral. Fasting LDL cholesterol will  
768 be measured at months 6 and 12 (Time 1 and 2 testing). However, in women with LDL-  
769 cholesterol > 190 mg/dl at month 6, a level for which the NCEP recommends therapeutic  
770 lifestyle changes and LDL-lowering drugs, we will re-assess fasting lipid profiles at months 8  
771 and 10. Should LDL again exceed 190 mg/dl on either determination, the subject will be  
772 withdrawn from the study and referred for treatment. If a subject develops coronary heart  
773 disease, venous thromboembolism, breast or endometrial or ovarian cancer, or biliary tract  
774 disease, she will be withdrawn from the study. Our plan to enroll only medically healthy  
775 perimenopausal women and to educate, encourage, and assess compliance with the AHA diet  
776 and exercise guidelines will minimize the development of medical conditions requiring  
777 withdrawal.

778 **General Statistical Considerations:** This is a two between subjects and one within-subjects  
779 (repeated measure) design. The two between-subjects factors are treatment (ERT or placebo,  
780 randomized) and history of DEP (positive or negative, non-randomized), and the within-subjects  
781 factor is time (psychiatric outcomes at months 0 (baseline), 1, 2, 4, 6, 8, 10, and 12, and CV  
782 measures at months 0, 6, 12). Analyses which use outcomes measured repeatedly will use this  
783 repeated measures design for analysis, with mixed models for continuous outcomes and logistic  
784 models for categorical outcomes. The mixed models we will fit will be random coefficient  
785 models, which treat the time variable as numerical. We do this for several reasons: (1) it allows  
786 for a finer assessment of precisely when women come in for a “visit,” as visits rarely take place  
787 on exactly the day planned, and (2) the covariance structure is necessarily simpler, leading to  
788 more efficient mixed models. For comparisons assessing change over time, we will assess this  
789 change as a difference between treatments or groups, as stated with respect to specific  
790 hypotheses, on differences between baseline and month 12 least squares means (LSMs). The  
791 month 6 CV data will be part of the mixed model predicting the 12 month least squares means.  
792 That is, the mixed model is an Intent- to-Treat analysis which uses all available data to make a  
793 prediction about what outcomes we would see if all subjects had remained in through the 12  
794 month endpoint. Several outcomes are measured or derived only once over the follow-up period  
795 (e.g., presence of at least one depressive episode during follow-up, or affective instability during  
796 the follow-up period). For those outcomes, the model will not include a repeated factor, and will  
797 be a two-factor ANOVA or logistic regression. For each analysis, where appropriate, we will  
798 perform sensitivity analyses by adding potential mediators, moderators, or confounders (see

799 D.4.3.) in an appropriate way to the model to assess the effect of these confounders, and to better  
800 define mechanisms, and subjects for whom, for example, treatment is effective. Most  
801 hypotheses will be examined as main effects, interactions, or contrasts. Prior to statistical  
802 analyses, we will use descriptive statistics and graphics to screen the data for errors, outliers, and  
803 potential influential observations, and to check distributional assumptions. We will not blindly  
804 switch to non-parametrics if distributions within groups do not appear to be normal, but will  
805 judge whether the type and degree of non-normality are such which require rethinking our  
806 modeling assumptions. We have a relatively large sample size and our linear models should be  
807 robust to relatively mild violations of normality. Even so, in the event we decide that the linear  
808 or linear mixed models we've selected are not appropriate, we will examine the possibility of  
809 testing hypotheses using permutation tests, sampling from the permutation distribution, in  
810 preference to non-parametrics.

811 We will define *affective instability* as the variance of each subject's CED-D total score over her  
812 follow-up period. We define the CV risk variable *Stress Reactivity*, as a composite formed in the  
813 following way: for IL-6, Mean Arterial Pressure, Vascular Resistance, and Cortisol, we will  
814 form the difference between resting and stress measures, yielding *reactivity* for each measure.  
815 We will calculate mean and SD for each measure at baseline (pre-treatment) and use those to  
816 standardize each measure at baseline (pre-treatment) and during the intervention to a common  
817 scale. We will then add the z-scores for the 4 measures together to form our stress reactivity  
818 composite at each point measured.

819 **Multiple Testing:** Several of the hypotheses use multiple outcome measures. We have in each  
820 identified one outcome as the primary outcome variable, and testing on this variable will be done  
821 without correction for multiple comparison. We will only examine other variables if the null  
822 hypothesis is rejected for the primary outcome variable. This enables us to follow significant  
823 effects with other analyses to explain or refine the response, helping us interpret the results.

824

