### 535 **Affective Well-Being Measures**

536 **1. Depression Episodes** will be operationalized in a manner consistent with other studies in  
537 perimenopausal depression and based on the following assessments: **The Center for**  
538 **Epidemiologic Studies Depression scale (CES-D)** is a 20-item self-report form assessing  
539 depressed mood. CES-D scores  $\geq$  16 have been consistently validated as defining high  
540 depressive symptoms suggestive of clinically significant DEP (positive predictive value=75%),  
541 and this cut-point has been used to define depressive episodes in multiple perimenopausal  
542 samples. Moreover, elevated CES-D scores have been shown to be sensitive to the anti-  
543 depressant actions of ERT in PM women. **Thus, CES-D scores  $\geq$  16 will be used to**  
544 **operationally define ‘depression episodes’.** However, if CES-D scores are  $>$  10 at any study  
545 visit then the Structured Clinical Interview for DSM-IV (non-patient edition) will be

546 administered to determine the presence of either minor or major depression. **Functional**  
547 **Impairment:** We will use the widely used Medical Outcomes Study 36-item short form (SF-  
548 36), which yields scores of general health perceptions, physical functioning, role limitations due  
549 to physical functioning, social functioning, bodily pain, general mental health, role limitations  
550 due to emotional problems, and vitality. The rationale for the selection of this instrument is  
551 based on: 1) the demonstration that it is sensitive to change over time; 2) its incorporation of  
552 subscales to specifically assess functional impairment related to emotional and physical  
553 symptoms as well as overall social functioning; 3) its able to discriminate subgroups of CVD  
554 patients known to have poorer survival and worse disease; and 4) normative data for this scale  
555 are available for the general US population as well as 13 medical conditions. **Symptom**  
556 **Severity and Affective Instability** will be assessed with the CES-D scale (at baseline and  
557 months 2,4,6,8,10 and 12), the former with a repeated measures approach and the latter by the  
558 variance in the CES-D score over 12 months.

559 **Lifetime Trauma Exposure** will be assessed by a validated interview. A cumulative (total)  
560 trauma score will be generated by assigning one-point for each of the following 15 traumas: **1)**  

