880 analyses of baseline data as two-group analyses rather than a main effect in a two-by-two  
881 factorial. The Stress Reactivity composite score as the response. If the null hypothesis is  
882 rejected, we will examine the same contrast for metabolic risk (as a parallel logistic regression  
883 model since it is categorical), flow mediated dilatation, and baroreceptor sensitivity.

884 **Aim 1 Hypothesis 2:** This secondary analysis will add the effect of trauma to the model, and  
885 assess whether trauma moderates the effect of DEP history on CV risk variables (above).

886 **Aim 2 Hypothesis 1:** In the mixed random coefficients model we will use for this repeated  
887 measures analysis, we will test this hypothesis using a contrast that examines the difference  
888 between the women with and without histories of DEP on the difference between the month 0  
889 and month 12 least squares means. This contrast will be done in the context of the full model but  
890 involves means from 2 of the 4 between-subjects cells. If this null hypothesis is rejected, we will  
891 test the same hypotheses for flow mediated dilatation and baoreceptor sensitivity (mixed model),  
892 and examine metabolic risk (categorical) via parallel logistic regression model.

893 **Aim 2 Hypothesis 2:** We will fit a two-factor logistic regression predicting the presence or  
894 absence of DEP episodes during the follow-up period. If we reject the null hypothesis, we will  
895 follow this with a two-factor mixed random coefficient model using CED-D, functional  
896 impairment and (using without the repeated measures portion since affective instability is  
897 defined over the entire follow-up period) affective instability as defined earlier. Further, as  
898 sensitivity analyses, we will examine the same effect on number of episodes / month during the  
899 follow-up period, using Poisson regression, and on the CES-D scores themselves using a mixed  
900 model.

901 **Aim 3 Hypothesis 1 (A and B):** With stress reactivity as the response, we will test these  
902 hypotheses in the context of the two between-factor one-repeated factor mixed random  
903 coefficient model we listed earlier. Hypothesis H1A is the main effect for treatment, predicting  
904 that the difference between the change in LSMs from month 0 to month 12 will be in different  
905 directions in the treated and untreated women. If this null hypothesis is rejected, we will examine  

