 934 regression on number of episodes, and for the analysis of the CES-D scores themselves.

935 **Aim 1, H1:** Our primary hypothesis for Aim 1 involves Stress Reactivity and since we cannot  
 936 assert that any stress-responsive factor is more important than another in this context, we will  
 937 combine different measures of stress-responsive CV risk factors and combine them into an index  
 938 called Stress Reactivity, described above. Since this measure has not been used before, we do  
 939 not have information from prior research on means and standard deviations which could help  
 940 with power and sample size calculations. Instead, we performed power calculations for each of  
 941 the stress reactivity variables which comprise the composite score. We used differences between  
 942 DEP and non-DEP groups from Pace et al. (Am J Psychiatry, 2006. **163**(9): p. 1630-3) for IL-6;  
 943 from Young et al. (Neuropsychopharmacology, 2000. **23**(4): p. 411-8) for cortisol; from  
 944 Brownley et al. (Am J Obstet Gynecol, 2004. **190**(4): p. 1052-8) for clinically relevant  
 945 differences in MAP; and from [name] (Health Psychol, 2007. **26**(2): p. 201-13; Int J  
 946 Psychophysiol, 1994. **17**(3): p. 233-48).for group differences in VRI – using the reported group  
 947 differences to define the magnitude of differences which are important, and to obtain estimates  
 948 of SDs. We obtained effect sizes of 0.63, 0.86, 1.0, and 1.5 for differences in delta MAP, VRI,  
 949 IL-6, and Cortisol, respectively. Our sample size of 160 per DEP group yields **99% power to**  
 950 **reject a null hypothesis** of no effect for an effect size of 0.63, (the smallest above), and 80%  
 951 power to detect an effect size as small as 0.40. Due to the complexity of the random coefficient

952 model to be used for this variable, we approximated our calculations with a simpler ANOVA  
953 power on change scores. Our actual power should be higher because the model should be more  
954 precise.

955 **Inducements for Participation**

956 Total possible monetary inducement for participating = \$1,275, prorated as follows:

957 \$100 for the medical and psychiatric screening (these screenings also provide benefit in the form  
958 of free medical evaluations)

959 \$150 for each laboratory test session (\$450 total)

960 \$100 for each flow mediated dilatation procedure (\$300 total)

961 \$ 25 for each interim study visit (\$125 total)

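### Aim 3 continuous cardiovascular contrasts: numeric time on months 0, 6 and 12 reduces to the raw change score, so adjusting for baseline would gain precision at almost no cost

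*Protocol*

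**What the plan says.** General Statistical Considerations (under Data Monitoring and Analysis) specifies random coefficient "models, which treat the time variable as numerical". The reasons given are exact visit timing and a simpler, more efficient covariance structure. Change over time is to be compared "on differences between baseline and month 12 least squares means (LSMs"). Month 6 is said to be part of the model that predicts month 12. The schedule is "measures at months 0, 6, 12" for cardiovascular outcomes. No baseline covariate or equal-baseline constraint is stated for the treatment comparison.

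The analytic plan for Aim 3 Hypothesis 1 applies this model to Stress Reactivity. H1A is the treatment contrast and H1B the history-by-treatment contrast. If H1A is rejected, metabolic risk (logistic), flow-mediated dilatation and baroreceptor sensitivity follow.

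The power section (Aim 1, H1) approximates the model by an ANOVA on change scores and adds: "Our actual power should be higher because the model should be more" precise.

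For CES-D the schedule is given in two ways. General Statistical Considerations has the within-subject "factor is time (psychiatric outcomes at months 0 (baseline), 1, 2, 4, 6, 8, 10, and 12, and CV" measures separately. Affective Well-Being Measures lists baseline and "months 2,4,6,8,10 and 12), the former with a repeated measures approach and the latter by the" variance, with no month 1.

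**The concern.** Stress Reactivity is the protocol's primary cardiovascular outcome, and H1A is the gate to the other cardiovascular outcomes. A reader would expect a mixed model that uses month 6 and is called efficient to do better than a change score. With three equally spaced visits and full data it does not. A change score carries the full noise of the baseline value into the treatment comparison. In a randomised comparison the baseline can be used to remove noise instead, and these values are already collected. At stake is precision on the gatekeeper test, not its validity.

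For repeated CES-D there is a second, smaller issue. A straight line through eight visits need not pass near the month-12 difference if benefit appears early and then holds.

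**Working it through.** **Inputs.** Visit times and contrast: General Statistical Considerations. 160 per arm: Randomization section. Two-sided 0.05: stated for Aim 3 H2, assumed here too. The correlation r and an effect size for treatment on Stress Reactivity are not given; r of 0.3 to 0.7 and 0.30 SD are assumptions, with equal SD at baseline and month 12.

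**The plan's own power figures.** With 160 per group, SE = √(2/160) = 0.1118 SD. Effect 0.63: 0.63/0.1118 = 5.63, power above 99.9% (stated 99%). Effect 0.40: 0.40/0.1118 = 3.58, power Φ(3.58 − 1.96), about 95%, against the stated 80%. The effect detectable with 80% power is (1.96 + 0.84) × 0.1118 = 0.313. This mismatch is a separate matter, and nothing below depends on it.

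**Cardiovascular contrast.** For balanced data with random intercept and slope, generalised and ordinary least squares agree. Times 0, 6, 12 have mean 6 and sum of squares 72. Fitted 12-month change = 12 × (−6·y0 + 0·y6 + 6·y12)/72 = y12 − y0, so the weights are (−1, 0, +1). A quadratic in time passes through all three means and gives the same weights. A simulated REML fit of the full two-by-two model on complete data confirmed it: −0.334649 (SE 0.11957) from the model and from the raw change score. With 20% missing at month 12 the two differed (SE 0.125 against 0.129).

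**Variance per arm, in units of s²/n.** Change score: 2(1 − r). Baseline-adjusted: 1 − r². Ratio: (1 + r)/2. The two-by-two interaction contrast with equal cells has the same ratio. If the SDs differ, change minus adjusted variance is (s0 − r·s12)², never negative.

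| r | change | adjusted | ratio | power, 0.30 SD: change → adjusted |
|---|---|---|---|---|
| 0.3 | 1.40 | 0.91 | 0.65 | 62% → 80% |
| 0.5 | 1.00 | 0.75 | 0.75 | 77% → 87% |
| 0.7 | 0.60 | 0.51 | 0.85 | 93% → 96% |

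Power is Φ(0.30/√(2v/160) − 1.96), with v the tabled variance. Example, r = 0.5: 0.30/0.1118 = 2.68 gives 77%; 0.30/√(1.5/160) = 3.10 gives 87%.

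**With dropout** (r = 0.5, compound symmetry; 5% missing month 6 and 15% missing month 12, then 12.5% and 25%): straight line 1.119 and 1.227; categorical visit without baseline adjustment 1.122 and 1.234; categorical visit with baseline adjustment 0.872 and 0.984. The gain comes from the baseline adjustment, not from treating visit as a category.

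**CES-D.** On the eight-visit schedule the times have mean 5.375 and sum of squares 133.875. The weights 12(t − 5.375)/133.875 are −0.48, −0.39, −0.30, −0.12, 0.06, 0.24, 0.42, 0.59. For an effect that rises linearly to a plateau, the share of the true month-12 effect recovered is:

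| plateau reached by | 8 visits | 7 visits (no month 1) |
|---|---|---|
| month 1 | 0.48 | 0.64 |
| month 2 | 0.68 | 0.64 |
| month 4 | 0.93 | 0.86 |
| month 6 | 1.05 | 1.00 |

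Under compound symmetry the straight-line variance is (144/133.875)(1 − r) = 1.076(1 − r). The baseline-adjusted categorical month-12 contrast has 1 − r², so it is (1 + r)/1.076 times as variable: 1.21, 1.40 and 1.58 at r = 0.3, 0.5 and 0.7. On seven visits (sum of squares 112) the multiples are 1.01, 1.17 and 1.32.

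**The case against.** A change contrast is unbiased under randomisation and lets one model serve Aims 2 and 3. That is true, and it makes this a question of precision only. The size of the gain also depends on assumed inputs: at 0.40 SD and r = 0.5, power moves only from about 95% to about 98.5%.

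Four stronger readings are tempting, and the protocol does not support them.

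- *H1A tests the arm difference at month 0.* The text "Hypothesis H1A is the main effect for treatment, predicting" might suggest this, since with time coded from zero the treatment term is the baseline difference. But the sentence goes on to define H1A as the difference between arms in least squares mean change from month 0 to 12. Main effect here means averaged over history, as opposed to the H1B interaction.
- *The claim of higher actual power is false.* It fails only for complete, on-schedule data. The protocol foresees withdrawals and uses all available data. With 15%, 20% or 25% missing only month 12 and r = 0.5, the line has variance 1.113, 1.158 and 1.207, against 1.176, 1.250 and 1.333 for change scores in completers: 5%, 7% and 9% less. The sentence can stand.
- *Visit as a category gives less variance throughout.* For CES-D under compound symmetry it gives more, as shown above.
- *The CES-D treatment result will be attenuated.* The protocol gives no time course. The 48% figure needs full benefit by month 1, while the amended schedule still has step-up strengths until week six. Gradual divergence is also plausible in a preventive setting. Repeated CES-D is a gated follow-on, and the any-episode logistic test of Aim 3 H2 is unaffected.

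**Conclusion.** The point holds for the randomised Aim 3 contrasts on Stress Reactivity, flow-mediated dilatation and baroreceptor sensitivity. With complete, on-schedule data the planned contrast is the raw change score. Adjusting for baseline would cut its variance by 35%, 25% or 15% at assumed r = 0.3, 0.5 or 0.7. With the dropout patterns examined at r = 0.5 the reduction is still about 20% to 22% (0.984/1.227 = 0.80; 0.872/1.119 = 0.78). The identity is exact from the visit schedule; the size of the gain rests on r. The model's advantage over change scores comes only through incomplete or off-schedule data.

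For CES-D the arithmetic shows possible understatement of a month-12 effect that levels off by months 1 to 4. Because the shape is assumed and the alternative is more variable, this supports a sensitivity analysis, not replacement of the model.

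**What to change.** 1. In the Aim 3 H1A and H1B models for continuous cardiovascular outcomes, constrain baseline means to be equal across treatment arms within depression-history stratum, or include baseline as a covariate alongside history. Keep the month-12 treatment and treatment-by-history contrasts.
2. Numeric time can stay. One cost to know: with a straight line and a constrained baseline, month 6 is no longer weighted zero. At r = 0.5 under compound symmetry the weights are −0.55, 0.18 and 0.91, so an effect already complete at month 6 is returned as 0.18 + 0.91 = 1.09 of its size. A quadratic treatment-by-time term, or baseline as a covariate, avoids this.
3. Leave Aim 2 on change: its history groups are not randomised.
4. For repeated CES-D, add a sensitivity analysis with visit as a category and report the month-12 contrast. State its cost: about 1.2 to 1.6 times the variance on eight visits (1.0 to 1.3 on seven), more covariance parameters, and windows for off-schedule visits. Reconcile the two CES-D schedules on month 1.
5. Optionally, note beside the power statement that the gain over change scores arises only from incomplete or off-schedule data.

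All of this is analysis wording and needs no new data.
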